5.4 ENROLLMENT/REGISTRATION OF PATIENTS

- 5.4.1 Patients must give written, informed consent prior to enrollment on this study. Informed consent may be obtained by the protocol chairman, the principal investigator at one of the additional sites, or one of their designees.

It is not uncommon for patients to have mental status changes related to their diagnosis of TTP (typically reversible with therapy) that may prevent them from being able to provide informed consent. If the principal investigator, co-investigator, or research study nurse do not feel the patient is able to provide informed consent, the study consent may be signed by the patient's legally authorized representative to enroll the patient in the study.

If the patient's legally authorized representative signs the consent, the patient must be then re-consented with the "re-consent form" if/when the patient regains the ability to provide informed consent.

- 5.4.2 Given concerns for the need to rapidly initiate, PE therapy should not be withheld while awaiting enrollment to this study. To allow sufficient time to evaluate for eligibility and obtain informed consent, patients will be permitted to be enrolled within 48 hours after the first PE procedure.

5.4.3 At the time of enrollment on this protocol, patients must be registered by phone with the study coordinating office at Ohio State University, the lead institution for this study. Contact information for all study personnel, protocol chairman, and co-investigators is detailed in section 15.0 of the protocol.

6.0 Randomization of Patients

6.1 Patients will be randomized at the time of registration/enrollment on this clinical trial via contact with the study nurse/coordinator at the time of the initial registration of the subject. The study statistician ([name]) will conduct the randomization and relay this information to the study nurse who will be in contact with the treating/enrolling physician so that the appropriate medication (prednisone or cyclosporine) may be immediately started with PE.

7.0 Treatment Plan: Initial Therapy

7.1 Therapeutic Plasma Exchange-Both Study Arms

7.1.1 Plasma exchange will be started as soon as the diagnosis of TTP has been made. (section 5.2.1). As it is important to institute therapy as soon as possible, patients will not have therapy delayed while obtaining informed consent.

7.1.2 Plasma exchange will be performed daily with one plasma volume exchanged using plasma as the replacement fluid until a complete remission is obtained (see response criteria 8.0).

7.1.3 Patients will receive either prednisone or cyclosporine orally as an adjunct to PE depending on the outcome of randomization (see sections 7.2-7.3 below). Therapy with these adjuncts will be initiated concurrent with and continue throughout plasma exchange therapy as described below.

7.1.4 After a complete remission (see response criteria 8.0) has been attained patients will have one exchange performed every other day for a total of 2 more exchanges, with the first day that the platelet count and LDH are normal counting as the first of the two exchanges.

7.2 Corticosteroid Study Arm

7.2.1 At the time of diagnosis, patients will be started on daily prednisone therapy at a dose of 1 mg/kg/day (rounded off to the nearest 20 mg multiple) concurrently with daily PE. Patients unable to take oral corticosteroids will be switched to an equivalent intravenous corticosteroid until they are able to take oral medications. Patients may receive intravenous corticosteroids at any time to urgently treat reactions to the

infused plasma and for prophylaxis against future reactions prior to the next TPE.

7.2.2 Prednisone should be continued at full dose for 30 days after the last PE procedure. Subsequently, patients should decrease the dose by 50% each week over 4 consecutive weeks, starting on day 31. All corticosteroids should be discontinued completely by the end of the 4 week taper (approximately 8 weeks total of corticosteroid therapy).

7.3 Cyclosporine (Neoral) Study Arm

7.3.1 As not all brands of cyclosporine can be used interchangeably due to the potential for inconsistencies in cyclosporine drug concentrations, physicians will use the Neoral brand of cyclosporine whenever possible. If an additional brand must be used, the patient must stay on that same brand of cyclosporine throughout the 6 month course as the differing brands cannot be used interchangeably.

7.3.2 At the time of diagnosis, patients will be started on daily cyclosporine (Neoral) therapy at a dose of 2-3 mg/kg/day (rounded to the nearest 50 mg increment) concurrent with daily plasma exchange. Doses will be administered in the capsule form. The total dose will be divided into twice daily dosing. For consistency and standardization of cyclosporine levels throughout the study, doses of Neoral (cyclosporine) should be given at 8 AM and 8 PM each day. Neoral (cyclosporine) should be taken on an empty stomach, and patients should not eat for at least 30 minutes after their dose of Neoral (cyclosporine). Cyclosporine will be continued for a total of six months of therapy and then discontinued.

7.3.3 Patients with renal insufficiency at presentation will have the dose of CSA modified to minimize any potential added nephrotoxicity of CSA. Patients with a serum creatinine of 2.5 mg/dl or greater will not begin therapy with CSA until the serum creatinine has fallen below this threshold. Patients with a serum creatinine of 1.5-2.5 mg/dl will have the CSA dose decreased by 50% until the serum creatinine has normalized (< 1.5 mg/dl). After renal function as measured by the serum creatinine has normalized patients will have the dose increased to the intended dose of 2-3 mg/kg/day.

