5.0 Patient Selection

5.1 Inclusion of Women and Minorities.

Entry to this study is open to both men and women ages 18 and older, of all racial and ethnic subgroups. This study will be conducted in accordance with the International Conference on Harmonisation and the Helsinki Guidelines.

5.2 Eligibility Criteria.

- 5.2.1 Patients with a clinical diagnosis of idiopathic TTP as defined by a microangiopathic hemolytic anemia and thrombocytopenia ($<100 \times 10^3$)
- 5.2.2 Additional components of the pentad (fever, renal and neurologic abnormalities) need not be present.
- 5.2.3 Additional explanations for the microangiopathic changes including DIC and malignancy should be excluded.
- 5.2.4 Patients with pregnancy associated TTP will be permitted on this therapeutic trial if the child is delivered prior to the initiation of therapy for TTP. However, female patients that are breastfeeding and are unwilling to discontinue breastfeeding at the time of enrollment will be excluded from this study (see section 5.3.5)
- 5.2.5 Patients with a previous diagnosis of TTP are eligible to be enrolled provided they meet eligibility criteria and have not been treated for TTP in the past 30 days.
- 5.2.6 Given the potential for nephrotoxicity with CSA, all patients must have a serum creatinine of ≤ 2.5 mg/dl prior to enrollment

5.3 Exclusion Criteria.

- 5.3.1 In light of concern for the prompt initiation of PE, all patients with suspected TTP may be enrolled on this trial. If it is subsequently found that the patient does not meet enrollment criteria, they will be removed and their spot replaced for study purposes. Patients removed from the

study after enrollment will continue to be followed longitudinally for 6 months to be monitored for safety and will be included in the safety database.

- 5.3.2 Patients with TTP clinically categorized as secondary to stem cell transplant and solid organ, bloody diarrhea associated, malignancy associated, and drug associated will not be enrolled on this therapeutic study.
- 5.3.3 Incarcerated patients will be excluded from the study due to the inherent difficulties in maintaining close follow-up for study purposes in patients who are incarcerated.
- 5.3.4 Any patients already being treated chronically with corticosteroids or cyclosporine and taking these at the time of their presentation will be excluded from this study.

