7.5 Dose Adjustments During Cyclosporine Therapy and Renal Insufficiency

7.5.1 Patients who subsequently develop renal insufficiency during the 6 month course of CSA (serum creatinine >1.5 , but ≤ 2.5 mg/dl) will have the dose decreased by 50% (see Appendix 2). The dose will be returned to the same planned dose (2-3 mg/kg) after the serum creatinine has returned to normal (<1.5 mg/dl). If patients do not tolerate the resumption of CSA to the full dose (recurrent increase in the serum creatinine, high CSA levels), patients should be maintained on the dose level that was able to achieve a therapeutic CSA levels without renal toxicity. Patients with a serum creatinine greater than 2.5 mg/dl will have the CSA held, and restarted only when the serum creatinine is ≤ 2.5 mg/dl, with the change in dosing schedule the same as described above.

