8.5 Treatment after Recurrences of TTP

8.5.1 Patients suffering exacerbations of TTP as described in the protocol (Section 6.4) after treatment on the corticosteroid arm of this study may then be treated with CSA concurrent with the resumption of plasma exchange at the same dose and schedule as described in the CSA arm of this randomized trial, assuming that they still meet enrollment criteria (including the serum creatinine). Patients will also discontinue the corticosteroids on the same day that CSA is initiated. Patients treated with CSA and PE for exacerbations of TTP will then be prospectively followed as described below (Section 9.3 – 9.5), but will be analyzed independently from the patients treated with CSA and PE as the upfront therapy.

8.5.2 Patients suffering a relapse (recurrence greater than 30 days after the last exchange procedure) whether during CSA or after completing 6 months of CSA will continue to be followed on this study for the purposes of gathering follow-up data, but may be treated at the discretion of the treating physician.

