9.2 Laboratory Studies During Plasma Exchange

- 9.2.1 During plasma exchange therapy, the following labs will be obtained daily (see Appendix 1):
 - CBC with a differential and platelet count
 - chemistry panel (Na, K, Cl, CO₂, Cr, BUN, Ca, and glucose) with LDH

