Appendix 1. Research Study Calendar

Time (weeks)	0	Day 3										CSA Stop	28
			1***	2	3	4	8	12	16	20	24		
Inpatient Treatment*		→*											
Clinic Visit**			X	X	X	X	X	X	X	X	X	X	
Clinical Studies													
CBC		→*	X	X	X	X	X	X	X	X	X	X	
Platelets		→*	X	X	X	X	X	X	X	X	X	X	
Smear Review													
Chemistry Panel		→*	X	X	X	X	X	X	X	X	X	X	
Total bilirubin	X												
Indirect bilirubin	X												
LDH		→*	X	X	X	X	X	X	X	X	X	X	
Haptoglobin	X												
PT	X												
PTT	X												
Fibrinogen	X												
Direct antibody test	X												
Liver function tests	X												
Cyclosporine Level	X**		X	X	X	X	X	X	X	X	X		
Biologic Samples****	X		X	X	X	X	X	X	X	X	X	X	

*Continue daily until remission and plasma exchange tapered and stopped.

**Cyclosporine levels start on day 3, then weekly until discharge.

*** Weekly visits begin after discharge from hospital.

**** Research samples: 10cc blood, 100cc plasma only at diagnosis at the outset of exchange procedure

[figure not shown]
[figure not shown]
Time (weeks)	40	52	64	76	88	100	112	124	136	148	160
Inpatient Treatment*											
Clinic Visit**	X	X	X	X	X	X	X	X	X	X	X
Clinical Studies											
CBC	X	X	X	X	X	X	X	X	X	X	X
Platelets	X	X	X	X	X	X	X	X	X	X	X
Smear Review											
Chemistry Panel	X	X	X	X	X	X	X	X	X	X	X
Total bilirubin											
Indirect bilirubin											
LDH	X	X	X	X	X	X	X	X	X	X	X
Haptoglobin											
PT											
PTT											
Fibrinogen											
Direct antibody test											
Liver function tests											
Cyclosporine Level											
Biologic Samples****	X	X	X	X	X	X	X	X	X	X	X

*Continue daily until remission and plasma exchange tapered and stopped.

**Cyclosporine levels start on day 3, then weekly until discharge.

*** Weekly visits begin after discharge from hospital.

**** Research samples: 10cc blood, 100cc plasma only at diagnosis at the outset of exchange procedure

Appendix 2. Algorithm for dose adjustment of cyclosporine for both elevated drug levels and renal insufficiency

*reduce cyclosporine dose if not already done. If previously dose reduced and stable serum creatinine, continue at same dose. If cyclosporine was previously held and the serum creatinine is now > 1.5 mg/dl but ≤ 2.5 mg/dl, restart at 50% of planned dose (1.0-1.5 mg/kg).

8.30.07 version

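### Minor, wrong as written: in 7.3.3 the range for withholding cyclosporine and the range for halving it both include a creatinine of 2.5 mg/dl, a value that 5.2.6 admits

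*Combined protocol and SAP*

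**What the plan says.** Section 7.3.2 of the protocol sets the CSA dose at "2-3 mg/kg/day (rounded to the nearest 50 mg increment) concurrent with daily plasma exchange". Section 7.3.3 then modifies the start for patients who present with renal insufficiency, in two consecutive sentences:

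- Withhold: "Patients with a serum creatinine of 2.5 mg/dl or greater will not begin therapy with CSA until the serum creatinine has fallen below this threshold".
- Half dose: "Patients with a serum creatinine of 1.5-2.5 mg/dl will have the CSA dose decreased by 50" per cent, until creatinine is back below 1.5 mg/dl.

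The neighbouring creatinine rules are:

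- Eligibility (5.2.6): "all patients must have a serum creatinine of ≤ 2.5 mg/dl prior to enrollment".
- During therapy (7.5.1): half dose above 1.5 and up to and including 2.5 mg/dl. Patients "greater than 2.5 mg/dl will have the CSA held, and restarted only when the serum creatinine is ≤ 2.5 mg/dl".
- Restart after a hold (Appendix 2 footnote): "If cyclosporine was previously held and the serum creatinine is now > 1.5 mg/dl but ≤ 2.5 mg/dl, restart at 50% of planned dose".
- Steroid-arm patients who have an exacerbation (8.5.1) may receive CSA under these terms: "same dose and schedule as described in the CSA arm of this randomized trial, assuming that they still meet enrollment criteria (including the serum creatinine").

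**The concern.** The withhold sentence includes 2.5 mg/dl in plain words. The half-dose sentence gives a range that ends at 2.5. A patient at that value is eligible, so a site can meet the case within the rules and find two instructions for the same first dose.

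At stake is a start/no-start limit for a drug whose nephrotoxic potential is the reason 5.2.6 gives for having a creatinine criterion. Two sites could treat identical patients differently, and each could cite 7.3.3 in support. This is a matter of dosing consistency and of judging protocol deviations. It does not bear on the statistical design.

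**Working it through.** No figure in the statistical section depends on this point, so the check compares ranges and then sizes the dose difference.

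**Step 1: the ranges (creatinine in mg/dl).**

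- Eligible (5.2.6): up to and including 2.5
- Do not begin (7.3.3): [2.5, ∞)
- Half dose at start (7.3.3): [1.5, 2.5]
- Half dose during therapy (7.5.1): (1.5, 2.5]
- Hold during therapy (7.5.1): (2.5, ∞)

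**Step 2: is the upper end of the 7.3.3 half-dose range included?** The protocol's own usage suggests that it is.

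- In 7.4.3 the CSA concentration bands are 401-500, 501-600 and greater than 600 ng/ml, so 500 and 600 belong to the hyphenated bands they close.
- In 7.3.3 normal is below 1.5, so the lower end of 1.5-2.5 is included.
- In 7.5.1 the corresponding band is written with an explicit ≤ at 2.5.

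**Step 3: the overlap.** [2.5, ∞) ∩ [1.5, 2.5] = {2.5}. Around the boundary:

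| Creatinine | Eligible (5.2.6) | 7.3.3 do not begin | 7.3.3 half dose | 7.5.1 half dose | 7.5.1 hold |
|---|---|---|---|---|---|
| 2.4 | yes | no | yes | yes | no |
| 2.5 | yes | **yes** | **yes** | yes | no |
| 2.6 | no | yes | no | no | yes |

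Only 2.5 falls under both sentences of 7.3.3. The protocol quotes creatinine to one decimal place (for example 1.5 mg/dl in 3.2 and 4.0), so 2.5 is an ordinary reportable result.

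**Step 4: the dose difference at 2.5.** Half of 2-3 mg/kg/day is 1.0-1.5 mg/kg/day, against 0. In milligrams this needs a body weight, which the documents do not give, and an order for halving and for the 50 mg rounding in 7.3.2:

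- Assumed 70 kg, halved then rounded: 70-105 mg becomes 50-100 mg/day.
- Assumed 70 kg, rounded then halved: 140-210 mg becomes 150-200 mg, and half is 75-100 mg/day.
- Assumed 50 kg: full dose 100-150 mg, half 50-75 mg/day (75 is a tie between 50 and 100 if rounding comes last).
- Assumed 100 kg: full dose 200-300 mg, half 100-150 mg/day.

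Over an assumed 50-100 kg, the choice is 0 versus roughly 50-150 mg/day.

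**Step 5: does another section settle it?** Section 5.2.6 decides who enters, not what dose is given. Section 7.5.1 and the Appendix 2 footnote place 2.5 on the half-dose side, but they govern patients already on CSA or restarting it. Nothing visible says which sentence of 7.3.3 governs a first dose at 2.5.

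**Step 6: reach.** The rule applies to starts in the CSA arm. If the same dose and schedule in 8.5.1 is taken to bring 7.3.3 with it, the overlap also reaches steroid-arm patients who start CSA after an exacerbation. That is an inference, because 8.5.1 is permissive and 7.3.3 speaks of presentation. The point does not rest on it.

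**The case against.** The best answer is that the two sentences address different questions. The first says when to start and the second says how much to give. At 2.5 a site can wait until creatinine is below 2.5, start at half dose, and return to full dose once it is below 1.5. That path respects both sentences, suits the section's stated aim of limiting nephrotoxicity, and gives the explicit inequality precedence over a hyphenated range. This stands as a possible reading. A reader might infer that a site at 2.5 is bound to break one of the two sentences; for this reason, the documents do not support that. But the sequence has to be supplied by the reader, and 7.5.1 and the Appendix 2 footnote, though written for a different stage, treat 2.5 as a half-dose value. A site that starts at half dose also has a reasonable case.

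A reader might also infer that, apart from 2.5 itself, the withhold sentence matters only if creatinine rises after the patient qualifies, because 5.2.6 caps entry at 2.5. The documents do not support this either. Section 5.3.1 lets patients with suspected TTP enrol before all criteria are confirmed. Section 5.4.2 allows enrolment up to 48 hours after the first exchange, so a presenting value can differ from the qualifying one. The sentence has work to do above 2.5.

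The Appendix 2 algorithm figure is not shown in the text available and might say how 2.5 is handled. That limits how firmly one can say that the whole protocol is silent. It does not remove the overlap within 7.3.3, which does not refer to that figure.

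Finally, the matter is small. That is correct, and it sets the severity.

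**Conclusion.** The concern holds as a minor drafting error. At a presenting creatinine of 2.5 mg/dl, section 7.3.3 supports two readings of the first CSA dose, none yet or half dose at once, for a patient whom 5.2.6 admits. The difference is 0 versus 1.0-1.5 mg/kg/day.

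The conclusion assumes that the 7.3.3 half-dose range includes its upper end, as usage elsewhere in the protocol suggests. It also assumes that the unseen figure does not override the text. The milligram figures rest on assumed body weights and only illustrate scale.

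The consequence is limited. It concerns one value, only in patients starting CSA, and neither reading gives full dose. Creatinine is in the panel for which 9.2.1 states "During plasma exchange therapy, the following labs will be obtained daily", so any wait would be reviewed each day while exchange continues. The documents give no frequency for a value of exactly 2.5, so no patient count can be stated. A reader might infer a conflict between 7.3.3 and the other creatinine sections; those govern eligibility or a later stage of treatment, so a difference in boundary is not in itself a contradiction. There is no effect on power, alpha or the analysis.

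**What to change.** Make the two ranges in 7.3.3 meet without overlapping. The clinical team should choose the direction, since the documents do not settle it for a first dose.

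- **Option A.** Withhold CSA only when creatinine is greater than 2.5 mg/dl, and begin once it is ≤ 2.5 mg/dl. A patient at 2.5 then starts at half dose. This uses the same side of the cut-off as 5.2.6, 7.5.1 and the Appendix 2 footnote.
- **Option B**, if a stricter limit is wanted for the first dose. Keep the withhold sentence and write the half-dose range as 1.5 to < 2.5 mg/dl. A patient at 2.5 then waits.

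Either option removes the overlap: under A, (2.5, ∞) and [1.5, 2.5] share no value; under B, [2.5, ∞) and [1.5, 2.5) share none. When making the edit, check that the Appendix 2 figure is consistent with the choice. The cost is one sentence, by amendment or site memo, with no change to sample size or analysis.

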7.4 Management of Cyclosporine Dosing and Concentrations

7.4.1 The optimal therapeutic concentration of CSA in TTP is not known. For the purpose of this study, the target CSA concentration will be identical to the accepted therapeutic CSA concentration at each institution(100-400 ng/ml at Ohio State University) when used as immunosuppressive therapy. As described below, dose adjustments of CSA will not be made to reach this goal, but rather the dosing will only be changed for patients with supratherapeutic concentrations or a decline in renal function. Only

trough concentrations should be used to adjust the CSA dose. If patients have already taken their CSA on the morning of the CSA concentration measurements, dose adjustments should only be made in clinical toxicity is present (hypertension, anxiety, diarrhea, emesis).

7.4.2 Cyclosporine levels (trough) will be monitored after the third day of therapy, weekly for the first 4 weeks of therapy and then monthly while they are taking CSA to monitor drug levels and minimize any potential nephrotoxic effects (see section 9.2, Laboratory Studies During Plasma Exchange) Patients should not take their CSA prior to having the CSA levels drawn, but should take their scheduled dose after their blood is drawn that day in order to check trough CSA levels. Trough levels of CSA should be obtained at 8 AM, at the same time the morning dose of CSA is to be given for hospitalized patients. CSA levels will then be obtained at each follow-up visit to monitor drug concentrations to minimize the potential for CSA toxicity. The CSA dose will not be increased based on these levels, only decreased or held as a response to potentially toxic levels of CSA.

7.4.3 Patients with trough CSA concentrations above the upper limit of normal will have the dose altered as described below and levels checked again in 3 days (see Appendix 2). Subjects with trough cyclosporine concentration of 401-500 ng/ml should decrease the dose of cyclosporine by 25% and recheck the trough concentration in 3 days. Subjects with cyclosporine concentrations of 501-600 ng/ml should decrease the dose by 50% and recheck the concentration in 3 days. Subjects with cyclosporine concentrations greater than 600 ng/ml should hold any further cyclosporine doses until the levels are rechecked in 3 days. If the cyclosporine concentration is now less than 600 ng/ml, a 50% dose reduction should be performed with future dose adjustments made depending on future cyclosporine concentration determinations as described above. Although there is a theoretical concern regarding the effect of daily plasma exchange on CSA levels, it has been reported that plasma exchange had no significant effect on measured CSA levels.(39)

